- Two-cohort, two-stage phase II trial of combination therapy (daratumumab, carfilzomib, lenalidomide, and dexamethasone [DKRd]) for newly diagnosed multiple myeloma patients
- Each cycle consists of 28 days
- After 4-6 cycles of therapy, transplant eligible patients will undergo stem cell collection
- Pre- and post-treatment bone marrow biopsies will be obtained for confirmation of diagnosis and correlative studies
- Patients will receive 8 cycles of induction combination therapy of DKRd. Patients will undergo evaluation for response at monthly intervals using IMW uniform response criteria (Kumar. et al. Lancet Oncol 2016) with SPEP, 24-hr UPEP (if applicable), serum free light chains (FLC), and immunofixation.
- Patients with <PR at completion of 4 cycles, will stop therapy and be taken off study treatment at completion of 4 cycles.
- Patients achieving >PR at end of 4 cycles, will continue to receive the planned total of 8 cycles of combination therapy
 - Patients obtaining CR/sCR at any point during cycles 1-8 in serum and urine will undergo MRD testing using multi-parametric flow cytometry.
- Upon completion of protocol therapy, eligible patients will be encouraged to proceed onto maintenance therapy or high dose therapy with stem cell rescue under a separate treatment protocol or standard of care. If clinically indicated, patients may need alternative therapy.
- After completion of protocol therapy, patients will remain on study for an additional 3 years for survival analysis, including annual MRD assessment when appropriate.

Treatment Plan (see schema below)

Cohort 1:

- Cycle 1 ONLY: Daratumumab 16 mg/kg days 1, 8, 15, and 22; Carfilzomib 20 mg/m² per dose, days 2 and 3; Carfilzomib 36 mg/m² per dose, days 8, 9, 15, and 16; Dexamethasone 20 mg/dose, days 1,2, 3, 8, 9, 15, 16, and 22 ; Lenalidomide 25 mg/day, days 2–21 every 28 days; Acetaminophen 650 mg; intravenous Diphenhydramine 25 mg. Montelukast 10 mg will be administered prior to the first 4 doses of Daratumumab.
- Cycle 2: Daratumumab 16 mg/kg days 1, 8, 15, and 22; Acetaminophen 650 mg; intravenous Diphenhydramine 25 mg.

- Cycles 3-6: Daratumumab 16 mg/kg days 1 and 15; Acetaminophen 650 mg; intravenous Diphenhydramine 25 mg.
- Cycles 7-8: Daratumumab 16 mg/kg day 1; Acetaminophen 650 mg; intravenous Diphenhydramine 25 mg.
- Cycles 2-8: Carfilzomib 36 mg/m² per dose, days 1, 2, 8, 9, 15, and 16
- Cycles 2-8: Lenalidomide 25 mg/day, days 1-21 every 28 days

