3.2 Proposed Study Investigation with Correlative Studies

Given the potent anti-myeloma activity of the KRd combination as demonstrated by rapid and deep remissions and the lack of a defined MTD, as a logical extension to the above mentioned studies, we have developed this phase II investigation in newly diagnosed MM employing carfilzomib at 20/36 mg/m² and 20/56 mg/m² with lenalidomide and dexamethasone in combination with daratumumab, administered over 8 twenty-eight day cycles.

After 4 or more cycles of treatment with DKRd, transplant eligible patients will be encouraged to undergo autologous stem cell harvesting. Harvested stem cells will be stored for future use at time of disease relapse or progression. All patients will receive combination therapy with DKRd. M-spikes and FLCs will be monitored every month. Patients achieving <PR after completion of 4 cycles of therapy will stop protocol therapy. Patients who are ≥ PR after 4 completed cycles will receive additional 4 (i.e. a total of 8) cycles of DKRd. At any point during protocol, if patients achieve CR/sCR by serum and/or urine assessments²⁵, patients will undergo bone marrow examination to confirm CR per standard criteria: a minimum of a bone marrow aspirate must be collected, however a biopsy can also be performed per institutional practice. The first pulled bone marrow sample will be sent for multi-parametric flow cytometry as a priority sample. Upon completion of protocol therapy, eligible patients will be encouraged to proceed onto maintenance therapy or high dose therapy with stem cell rescue under a separate treatment protocol or standard of care. Some patients may need alternative therapy after completing protocol therapy.

Collected bone marrow and peripheral blood samples will be processed and stored to create a sample bank used to later evaluate biological activity of daratumumab, carfilzomib, lenalidomide, and dexamethasone.

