5.4 Daratumumab

DARZALEX™ (daratumumab) is a human immunoglobulin G1 kappa (IgG1κ) monoclonal antibody (mAb) that binds with high affinity to a unique epitope on CD38, a transmembrane glycoprotein. It is a targeted immunotherapy directed towards tumor cells that express high levels of CD38, in a variety of hematological malignancies including MM, leukemia, and non-Hodgkin's lymphoma (NHL).

Daratumumab induces lysis of CD38-expressing tumor cells, by a wide spectrum of mechanisms including complement-dependent cytotoxicity (CDC), antibody-dependent cell-mediated cytotoxicity (ADCC), and antibody-dependent cellular phagocytosis (ADCP), through activation of complement proteins, natural killer (NK) cells, and macrophages, respectively [de Weers 2011, Overdijk 2013]^{2,20}. For the most comprehensive nonclinical and clinical information as well as Reference Safety Information regarding daratumumab, refer to the latest version of the Investigator's Brochure [Daratumumab IB].

Preliminary pharmacodynamic studies suggest that daratumumab utilizes multiple effector cell functions, resulting in immune mediated killing of CD38-expressing tumor cells. In ex vivo experiments utilizing human bone marrow stromal cells co-cultured with primary CD38-expressing MM cells, complement-dependent cytotoxicity (CDC) occurs rapidly and demonstrates maximal myeloma cell killing by daratumumab within 1 hour of antibody-mediated activation of the complement proteins (de Weers 2011)². Daratumumab-induced antibody-dependent cell-mediated cytotoxicity (ADCC) is slower in its action, with maximal ADCC by daratumumab observed at 4 hours in vitro (de Weers 2011)². Daratumumab has also been shown to induce antibody-dependent cellular phagocytosis (ADCP) in the presence of macrophages within 4 hours in vitro (Overdijk 2013)²⁰. Further, in vitro studies indicated that daratumumab inhibited the cyclase activity of CD38 and stimulated the CD38 hydrolase activity (Study No. GMB 3003-013).

Studies on proliferation of and release of cytokines in human blood cells have indicated that daratumumab does not exert target-specific agonistic activity. The cytokine release observed is mainly caused by the Fc-portion of IgG1 and comparable to that of approved therapeutic antibodies already in clinical use. Specific binding of daratumumab was detected in multiple tissues of both human and chimpanzee origin.

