Flow cytometry: Immunophenotyping of aberrant plasma cells by flow cytometry currently involves, but is not limited to, the use of the following reagents: CD138, CD19, CD45, CD38, and CD56.

Characteristic changes in immunophenotypically abnormal plasma cells (CD38 bright and/or CD138 positive) include but are not limited to decreased or absent CD19 and CD45, decreased CD38, increased CD56, decreased CD27, decreased CD81, increased CD117. For patients with non-evaluable samples at MRD assessment, patients can opt for repeat MRD assessment or continue to receive a total of 8 cycles of CRd. The first pulled bone marrow sample will be sent for multi-parametric flow cytometry as a priority. Samples will undergo MRD testing per MSK institutional practice, see section 12.0 for further methodology practice.

Molecular pathology: For MRD samples utilizing the NGS LymphoSIGHT™ (Adaptive, CA) platform, the InVivoScript NGS platform, immunoglobulin heavy and kappa chain variable, diversity, and joining gene segments from genomic DNA obtained from CD138+ bone marrow (BM) cell lysate or cell-free supernatant BM aspirate were amplified using universal primer sets as described elsewhere²¹. An MM clonotype was defined as an immunoglobulin rearrangement identified by NGS.

Mass spectrometry based proteomics for minimal residual disease assessment: Serial urine and serum samples will be analyzed to detect clonotypic peptides representing patient's monoclonal immunoglobulin heavy and light chains using high resolution mass-spectrometry-based proteomics.

FISH and cytogenetics

Interphase FISH/cytogenetics will be performed on patients enrolled in this protocol.

DNA-based target mutations

Bone marrow aspirate samples will be analyzed for somatic mutations by exome-sequencing of targeted genes using MSK *myTYPE* platform (or equivalent e.g. MSK Impact Heme). After therapy, perform if response is \leq PR or evidence of gross residual disease on SPEP/UPEP

Cell Sorting and Bone marrow cell lysate

Bone marrow aspirate storage samples will be sorted into CD 138 + and CD 138 – fractions and whole bone marrow cell lysate per HOTB SOP.

Research Blood/Serum and Urine

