For patients undergoing MRD or end of study assessment, the first pulled bone marrow sample will be sent for multi-parametric flow cytometry as a priority. This will be a centralized Next-Gen Sequencing (NGS) based MRD testing. Flow cytometry based assay to rule out MRD (defined as less than 20 abnormal plasma cells) in bone marrow aspirates of CR/sCR/VGPR patients. CR/VGPR and MRD 10^{-5} negative in the bone marrow is confirmed by using a validated method with a sensibility of at least 1 in 10^{-5} nucleated cells. Patients with $< \text{CR/sCR/VGPR}$ are considered MRD positive. We will use the MSKCC flow cytometry MRD method which is based 10-colors in a single tube. This test has sensitivity to identify 1 myeloma cell in 100,000 bone marrow cells, or better. The test demonstrates highly similar results when compared to the current Euroflow approach. This test is validated and already in clinical use at MSK. Immunophenotyping of aberrant plasma cells by flow cytometry currently involves, but is not limited to, the use of the following reagents: CD138, CD19, CD45, CD38, and CD56. Characteristic changes in immunophenotypically abnormal plasma cells (CD38 bright and/or CD138 positive) include but are not limited to decreased or absent CD19 and CD45, decreased CD38, increased CD56, decreased CD27, decreased CD81, increased CD117. For patients with non-evaluable samples at MRD assessment, patients can opt for repeat MRD assessment or continue to receive a total of 8 cycles of DKRd. A patient with CR/sCR/VGPR who has undeterminable MRD status will be treated as MRD+ for the primary endpoint.

Traditional Response Criteria from International Myeloma Working Group Criteria for Multiple Myeloma⁶⁵ (KUMAR ET AL, LANCET ONCOL 2016):

Evaluation of Response Criteria

- a) Stringent Complete Response (sCR)
 - Complete Response as defined below plus: Normal FLC ratio and absence of clonal cells in bone marrow by immunohistochemistry or immunofluorescence (presence/absence of clonal cells is based on the kappa/ lambda ratio).
- b) Complete Response (CR)
 - Negative immunofixation on the serum and urine and disappearance of any soft tissue plasmacytomas and $\leq 5\%$ plasma cells in bone marrow
- c) Very Good Partial Response (VGPR)

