 - Serum and urine M-protein detectable by immunofixation but not on electrophoresis or 90% or greater reduction in serum M-protein plus urine M- protein level <100 mg per 24h. If the serum and urine M-protein are unmeasurable, a $\geq 90\%$ decrease in the difference between involved and uninvolved FLC levels is required in place of the M-protein criteria.
- d) Partial Response (PR)
 - $\geq 50\%$ reduction in M protein and reduction in 24-h urinary M-protein by $\geq 90\%$ or to < 200 mg per 24h . If the serum and urine M-protein are unmeasurable, a $\geq 90\%$ difference between involved and uninvolved FLC levels is required in place of the M-protein criteria
- e) Stable Disease (SD)
 - Not meeting criteria for CR, VGPR, PR or progressive disease. All categories also require no known evidence of progressive or new bone lesions if radiographic studies were performed. Radiographic studies are not required to satisfy these response requirements.
- f) Progressive disease (PD)
 - Requires any one or more of the following:
 - Increase of $\geq 25\%$ of nadir in:
 - Serum M-component and/or (absolute increase must be ≥ 0.5 g/dl. The serum M-component increases of ≥ 1 gm/dl are sufficient to define relapse if starting M-component is ≥ 5 gm/dl.
 - Urine M-component and/or (the absolute increase must be ≥ 200 mg/24h
 - Only in patients without measureable serum and urine M-protein levels: the difference between involved and uninvolved FLC levels. The absolute increase must be >10 mg/dl.
 - Bone marrow plasma cell percentage: the absolute % must be $\geq 10\%$
 - Definite development of new bone lesions or soft tissue plasmacytomas or definite increase in size of existing bone lesions or soft tissue plasmacytomas
 - Development of that can be attributed solely to the plasma cell proliferative disorder

g) Relapse from CR

- Any one or more of the following:
 - Reappearance of serum or urine M-protein by immunofixation or electrophoresis. (Appearance of monoclonal or oligoclonal bands that are different from original isotype may not be defined as “relapse from CR”. Often times, such bands may indicate fluctuations in immunological parameters that are not reflective of MM disease. In these situations, immunofixation and electrophoresis will be interpreted by the clinician before being labeled as “relapse”^{27,28}.
 - Development of $\geq 5\%$ light-chain restricted plasma cells in the bone marrow

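### CR/sCR requires negative serum immunofixation while every patient is on an IgG1 kappa antibody, and no rule covers a drug band in IgG-kappa myeloma: the CR/sCR rate can be understated

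*Combined protocol and SAP*

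**What the plan says.** Section 12.0 requires for CR "Negative immunofixation on the serum and urine and disappearance of any soft tissue plasmacytomas", plus a plasma-cell limit in the marrow. sCR is "Complete Response as defined below plus: Normal FLC ratio and absence of clonal cells in bone marrow", so it inherits the immunofixation condition. Neither definition mentions a band from a therapeutic antibody.

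Section 5.4 says that daratumumab "is a human immunoglobulin G1 kappa (IgG1κ) monoclonal antibody (mAb) that binds with high affinity". Section 3.2 says "All patients will receive combination therapy with DKRd", and the Section 9.0 schedule gives daratumumab in each of cycles 1-8 in both cohorts. Section 9.4.1 places the myeloma tests, including serum electrophoresis and immunofixation, on Day 1 of each cycle and at end of therapy. Section 12.0 (Disease Parameters, item d) requires two consecutive determinations before a response is classified.

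The CR reading also starts a procedure. Section 1.0 states: "Patients obtaining CR/sCR at any point during cycles 1-8 in serum and urine will undergo MRD testing using multi-parametric flow cytometry".

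Section 12.0 has one exception for misleading bands, under Relapse from CR: "Appearance of monoclonal or oligoclonal bands that are different from original isotype may not be defined as" relapse. The only assay interference by daratumumab that the protocol acknowledges is with the indirect antiglobulin test (Section 11.4). Mass spectrometry is planned in Section 10.0 ("Serial urine and serum samples will be analyzed to detect clonotypic peptides"), but Section 14.0 uses it only for concordance with flow cytometry as an MRD technique.

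**The concern.** Immunofixation identifies heavy- and light-chain class. A circulating IgG1 kappa antibody can therefore show as an IgG-kappa band. The documents do not say this; it follows from the isotype that they give and from what the test detects. In a patient with IgG-kappa myeloma, such a band has the isotype of the original disease. Applied as printed, Section 12.0 then withholds CR from a patient whose myeloma protein has gone, and VGPR is recorded instead.

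Two things are at stake. First, the CR/sCR rate is a named secondary endpoint, reported per cohort with an exact 95% confidence interval, and that interval does not allow for systematic misclassification. The natural benchmark in Section 3.0, 56% sCR/CR in the earlier KRd study, comes from a regimen without daratumumab, so a comparison with it would be tilted against the new regimen. Second, the on-treatment MRD marrow may come later in these patients. Section 3.0 already reports average cycles to MRD negativity by cohort, a measure that depends on when the marrow is taken.

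**Working it through.** **1. The plan's own figures.** The earlier KRd rate is 25/45 = 55.6%, printed as 56%. Section 14.0 gives no target or precision for CR/sCR. Its only design figure is the two-stage rule for the primary endpoint (28 then 41 patients, continue at 12 or more, success at 21 or more, 40% versus 60%). An exact binomial calculation returns type I error 0.0951 and power 0.9009, so that figure reproduces. Nothing below changes N = 41.

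**2. Size of the understatement.** Let C be the true CR/sCR rate, k the share of patients with IgG-kappa disease, and i the share of their true CRs that are masked.

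Recorded rate = C × (1 − k × i); understatement = C × k × i.

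C = 0.56 is the Section 3.0 figure used for illustration. The documents give neither k nor i, so both are assumptions: k 25-45%, i 10-100%.

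| k | i | Understatement | Recorded rate |
|---|---|---|---|
| 25% | 10% | 0.56 × 0.25 × 0.10 = 1.4 points | 54.6% |
| 35% | 50% | 0.56 × 0.35 × 0.50 = 9.8 points | 46.2% |
| 45% | 100% | 0.56 × 0.45 × 1.00 = 25.2 points | 30.8% |

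In a cohort of 41, the middle row means about 19 recorded CRs (41 × 0.462 = 18.9) instead of 23 (41 × 0.56 = 23.0). The exact 95% interval is 30.7-62.6% instead of 39.7-71.5%.

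**3. How long a drug band could last.** This step uses the Section 9.0 schedule with no delays: 18 doses of 16 mg/kg, on days 0-49 weekly, days 56-154 every 14 days, then days 168 and 196, counting cycle 1 day 1 as day 0. Assumptions not in the documents are distribution volume V of 45, 60 or 90 mL/kg, half-life h of 9, 14 or 20 days, and an immunofixation limit of 0.01-0.03 g/dL.

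Level at day t, in g/dL = 0.1 × Σ (16/V) × 0.5^((t − dose day)/h), summed over earlier doses, for the nine combinations of V and h.

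| Reading (pre-dose) | Range, g/dL | At or above 0.01 | At or above 0.03 |
|---|---|---|---|
| Cycle 3 day 1 (day 56) | 0.025-0.111 | 9 of 9 | 8 of 9 |
| Cycle 4 day 1 (day 84) | 0.011-0.077 | 9 of 9 | 5 of 9 |
| Cycle 5 day 1 (day 112) | 0.009-0.065 | 8 of 9 | 4 of 9 |
| Cycle 8 day 1 (day 196) | 0.003-0.036 | 5 of 9 | 1 of 9 |
| End of cycle 8 (day 224) | 0.002-0.027 | 5 of 9 | 0 of 9 |

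A band is plausible through the middle cycles and uncertain at the end. Complete masking (i = 100%) would need the lowest detection limit and slow clearance in every patient, so 25.2 points is a ceiling.

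**4. Direction.** A drug band can turn a true negative immunofixation into a positive one. It cannot do the reverse, so the error from this source has one sign.

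**The case against.** The strongest reply has four parts.

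- *The endpoint is best response.* A band that fades delays CR without removing it, and at day 224 the modelled level straddles or falls below the assumed detection limit. This stands, and it is why the upper end is only a ceiling. It is weakened by the need for two consecutive determinations: at a limit of 0.01 g/dL, the same five of nine scenarios are at or above it on both day 196 and day 224. Section 9.4.1 lists no further myeloma tests until one year after therapy.
- *The primary endpoint is safe.* A reader might infer that lost CR marrows lower the MRD-negativity rate. If every masked patient also had no end-of-therapy marrow, a true 60% rate would become 0.60 × (1 − k × i), and power would fall from 0.90 to 0.73 at k = 35%, i = 25%. The documents do not support that reading. Section 12.0 allows MRD negativity in VGPR, its VGPR definition admits protein seen only on immunofixation, and Section 9.4.4 plans a marrow at end of therapy. What remains is that footnote h of Section 10.0 only encourages some marrows.
- *VGPR is safe too.* A reader might infer that drug alone could hold a patient entering at 1.0 g/dL above the 90% reduction mark of 0.1 g/dL. Pre-dose drug exceeds 0.1 g/dL in one of nine scenarios, at cycle 3 day 1 only (0.111), and never later. For a best-response endpoint the argument fails.
- *The rule may exist elsewhere.* Section 12.0 cites the 2016 IMWG criteria, and laboratory practice at this single centre is not described. That is possible, but the printed criteria contain no such rule.

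**Conclusion.** The point holds as a one-directional risk to a descriptive secondary rate. The printed CR/sCR definition can misclassify a true CR in IgG-kappa myeloma as VGPR, or date it late, and no rule in the documents prevents this. The CR-triggered MRD marrow may be postponed in the same patients.

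The size cannot be settled from the documents. The range of 1.4 to 25.2 points rests on a 56% true rate, an assumed IgG-kappa share of 25-45% and assumed masking of 10-100%. The premise that the drug shows on immunofixation is an inference from its isotype. Confidence is firm on direction and limited on magnitude.

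Stronger readings go too far. The documents do not show a bias in the primary endpoint, nor a material effect on the rates of VGPR or better or PR or better. Nor is there a basis for extending the figures to every isotype: the CR text is not limited to the original isotype, but a band of a class other than the patient's own can be recognised as different. This merits a clarifying amendment; it is not a flaw in the trial's main design.

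**What to change.** Add to Section 12.0: in a patient with IgG-kappa myeloma whose only remaining serum finding is a faint IgG-kappa band while on daratumumab, the band is checked against the patient's own clonotype, using the serum mass spectrometry already planned on the serial samples.

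Add to Section 14.0, secondary objective 2: report the CR/sCR rate with its exact 95% confidence interval twice per cohort, once by the printed criteria and once with bands shown not to be the patient's clone counted as immunofixation negative. The gap between the two shows the size of the problem in this trial. Leave the VGPR rule, the marrow schedule and the primary endpoint as they are.

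The cost is amendment wording and some planned mass spectrometry run earlier, with no new blood draws and no change to N = 41. The plan must also state the assay's performance for this use, since the documents give none. Reporting both rates keeps the printed-criteria result visible and avoids making mass spectrometry the sole arbiter of CR.

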6.1 Subject Inclusion Criteria

- Newly diagnosed patients with histologically confirmed MM based on the following criteria:
 - Clonal plasma cells in the bone marrow
 - Measurable disease within the past 4 weeks defined by any one of the following:
 - Serum monoclonal protein ≥ 1.0 g/dL
 - Urine monoclonal protein >200 mg/24 hour
 - Involved serum immunoglobulin free light chain > 10 mg/dL AND abnormal kappa/lambda ratio
- Evidence of underlying end organ damage and/or myeloma defining event attributed to underlying plasma cell proliferative disorder meeting at least one of the following:
 - Hypercalcemia: serum calcium >0.25 mmol/L (> 1 mg/dL) above upper limit of normal or ≥ 2.75 mmol/L (11 mg/dL)
 - Anemia: hemoglobin value <10 g/dL or > 2 g/dL below lower limit of normal
 - Bone disease: ≥ 1 lytic lesions on skeletal X-ray, CT, or PET-CT. For patients with 1 lytic lesion, bone marrow should demonstrate $\geq 10\%$ clonal plasma cells
 - Clonal bone marrow plasma cell percentage $\geq 60\%$
 - Involved/un-involved serum free light chain ratio ≥ 100 and involved free light chain >100 mg/L.
 - > 1 focal lesion on magnetic resonance imaging study (lesion must be >5 mm) in size
- Creatinine Clearance ≥ 60 ml/min. CrCl can be measured or estimated using Cockcroft-Gault method, MDRD, or CKD-EPI formulae
- Age ≥ 18 years at the time of signing the informed consent documentation
- Eastern Cooperative Oncology Group (ECOG) performance status 0-2
- Absolute neutrophil count (ANC) ≥ 1.0 K/uL, hemoglobin ≥ 8 g/dL, and platelet count ≥ 75 K/uL, unless if cytopenias are deemed to be due disease at discretion of clinical investigator. Transfusions and growth factors are permissible.
- Adequate hepatic function, with bilirubin < 1.5 x the ULN, and AST and ALT < 3.0 x ULN.

- All study participants must be able to tolerate one of the following thromboprophylactic strategies: aspirin, low molecular weight heparin or warfarin (coumadin) or alternative anti-coagulant.
- All study participants must be registered into the mandatory eREMS® program, and be willing and able to comply with the requirements of REMS®.

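### The printed CR definition has no free-light-chain condition, so a patient measurable only by FLC can be scored CR with a response shallower than the protocol's own VGPR

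*Combined protocol and SAP*

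**What the plan says.** **Entry.** Section 6.1 asks for "Measurable disease within the past 4 weeks defined by any one of the following". The third route is "Involved serum immunoglobulin free light chain > 10 mg/dL AND abnormal kappa/lambda ratio". FLC alone is therefore enough to enter, and Section 12.0, Disease Parameters a), treats such disease as measurable.

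**Response categories, Section 12.0.**
- CR: "Negative immunofixation on the serum and urine and disappearance of any soft tissue plasmacytomas", with at most 5% plasma cells in the marrow. No FLC term is printed.
- sCR: "Complete Response as defined below plus: Normal FLC ratio and absence of clonal cells in bone marrow". This is the only place where a normal FLC ratio is required, and it comes on top of CR.
- VGPR: if serum and urine M-protein are unmeasurable, a 90% or greater "decrease in the difference between involved and uninvolved FLC levels is required in place of the M-protein criteria".
- PR: in the same situation, a 90% or greater "difference between involved and uninvolved FLC levels is required in place of the M-protein criteria". The figure is the same as for VGPR, and the word decrease is absent.
- Progression: also has an FLC rule for patients without measurable M-protein.
- Stable disease: the remainder when none of the other categories is met.

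**General FLC text.** Disease Parameters b) says that FLC should be used to assess response when it is the primary determinant. Item d) requires the FLC result of such a patient to be confirmed on two consecutive determinations.

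**Where the label is used.** Section 1.0 states: "Patients obtaining CR/sCR at any point during cycles 1-8 in serum and urine will undergo MRD testing using multi-parametric flow cytometry". Under Minimal Residual Disease in Section 12.0, flow MRD is read in CR, sCR and VGPR patients, and patients below those categories count as MRD positive. Section 14.0 reports CR or sCR as one rate and counts best MRD response within 8 cycles against 12 of 28 and 21 of 41.

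**The concern.** A response scale is normally ordered, so that anyone in CR has also met VGPR. For FLC-only patients the printed scale does not guarantee this. VGPR tests the one marker that was measurable at entry. CR tests immunofixation, which in some of these patients may already have been negative before treatment.

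The label does two jobs. It enters the CR/sCR rate directly. It also opens the gate to the primary endpoint: a patient below VGPR is MRD positive by rule, whereas a patient labelled CR is judged on the flow result. Timing matters too. Under Section 10.0, footnote h, once a CR/sCR marrow is MRD negative, the end-of-study marrow follows standard of care, so an early label may not be rechecked on a fixed schedule.

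**Working it through.** **1. The plan's own design figures.** Inputs from Section 14.0: null rate 0.40, alternative 0.60, 28 then 41 patients, continue at 12 or more, success at 21 or more.

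P(success | p) = sum over x from 12 to 28 of Bin(x; 28, p) × P(Bin(13, p) ≥ 21 − x)

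- p = 0.40: 0.0951 (limit 0.10); probability of stopping at stage 1 is 0.551.
- p = 0.60: 0.9009 (target 0.90).

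A search over designs returns the same 28/41 design with cut-offs 12 and 21 as minimax. The design reproduces; the problem is in the definition that feeds the count.

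**2. One record scored against the printed text.** Illustrative values: FLC is the only measurable disease; the difference between involved and uninvolved FLC is 200 mg/L at baseline and 80 mg/L now; the ratio is still abnormal; serum and urine immunofixation are negative; marrow plasma cells are 4%; there is no plasmacytoma.

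Fall = (200 − 80)/200 = 60%. A 90% fall would need 200 × 0.10 = 20 mg/L or less.

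| Category | Test as printed | Result |
|---|---|---|
| sCR | CR plus normal ratio and no clonal marrow cells | not met |
| CR | immunofixation negative, no plasmacytoma, marrow ≤5% | met |
| VGPR | FLC difference down ≥90% | not met |
| PR | FLC difference ≥90%, as printed | not met |

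Nothing in Section 12.0 says that CR also requires VGPR or PR. The record is CR and passes the MRD gate. Scored on the VGPR criterion, it would be below VGPR and MRD positive by rule.

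**3. Does the CR-below-VGPR result depend on the PR wording?** No. It uses only the CR and VGPR text. The PR row does depend on it: if PR used 50%, the reduction printed for M-protein, the 60% fall would meet PR.

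**4. Size per patient.** CR/sCR rate: 1/41 = 2.4 percentage points. Primary count: also one patient, but only if the flow result is negative. The final rule separates 20/41 = 48.8% from 21/41 = 51.2%, and the stage 1 rule separates 11/28 = 39.3% from 12/28 = 42.9%. One wrongly credited patient changes a decision only at those boundaries.

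**5. Sensitivity, on assumptions only.** The documents give neither the FLC-only share nor the share misclassified. Suppose 5–20% of a cohort were FLC-only and 10–25% of those became false MRD-negative successes. The added null rate is 0.05 × 0.10 = 0.005 to 0.20 × 0.25 = 0.05. The effective null rate is then 0.405 to 0.45, and the formula in step 1 gives a type I error of 0.107 to 0.256. The upper end needs about 0.05 × 41 = 2 patients per cohort who are literally CR, below VGPR on FLC and flow-negative. The documents offer no evidence for that.

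**The case against.** The strongest reply is that Section 12.0 already brings FLC in. Item b) says it should be used in assessing response for exactly these patients, and item d) requires the FLC result itself to be confirmed. It would therefore be wrong to say that the confirmation rule looks only at immunofixation. Section 1.0 lists FLC among the monthly response tests, Section 3.2 confirms CR by standard criteria, and Section 12.0 cites the 2016 International Myeloma Working Group criteria. A careful assessor could withhold CR from the record above.

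That stands as mitigation, but it does not close the gap. None of this text states what FLC result CR requires or that categories are nested, so two assessors could score the same record differently. The cited standard is not before us, and the protocol prints its own definitions.

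Four stronger readings are tempting, and the documents do not support them:

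- *The patient also fails PR, so is both CR and due to stop after cycle 4.* This rests on the printed 90% in the PR text. The wording needs reconciling, but the conflict cannot be taken as settled.
- *The primary result is inflated.* A CR label does not make a patient MRD negative. Flow must be negative, and undeterminable status counts as positive. A patient labelled early who later meets the VGPR FLC criterion and is flow-negative within 8 cycles is counted correctly.
- *Several patients per cohort are affected.* Assuming 5–20% FLC-only and 25–50% misclassified gives 41 × 0.05 × 0.25 = 0.5 to 41 × 0.20 × 0.50 = 4.1 patients. Both ranges are guesses. Unmeasurable M-protein (below 1 g/dL in serum and 200 mg/24 h in urine) is also not the same as negative immunofixation, so the exposed group is only part of the FLC-only group.
- *CR must require a normal FLC ratio.* The protocol prints that requirement for sCR only.

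**Conclusion.** The point holds as a definitional gap. For patients measurable only by FLC, the printed CR can be met with a shallower response than the printed VGPR, and applying the CR text as written gives the wrong order. This follows from the CR, VGPR and entry text alone.

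The main effect is on the CR/sCR rate, at 2.4 points per misclassified patient in a cohort of 41, and on the rule that sends patients below VGPR to MRD positive. The effect on the 12/28 and 21/41 counts is limited to such patients who are also flow-negative. How many there are cannot be derived from the documents; the type I error range in the working is conditional on its assumptions and is not an estimate. The change should be made because it is cheap and removes a matter of judgement from an endpoint gate. It is not a reason to doubt the design.

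**What to change.** Add one sentence to Section 12.0 b): *where serum and urine M-protein are unmeasurable at baseline, CR additionally requires that the VGPR free-light-chain criterion be met.* State that the response categories are nested. Any further FLC-ratio requirement for CR is for the sponsor to set from the response standard it cites.

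Apply the same definition wherever the CR label is used: the marrow trigger in Sections 1.0 and 3.2, and the MRD gate in Section 12.0.

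At the same time, reconcile the PR FLC wording (the same 90% as VGPR, with no word for decrease) and the rule on patients below PR after cycle 4 with this definition, so that one record cannot fall under two rules.

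Cost: a short amendment to Section 12.0. FLC is already measured on Day 1 of every cycle (Section 9.4.1), so no new data are needed, and sample size and cut-offs do not change. The CR/sCR rate may be slightly lower.
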